6.7 MULTIPLE COMPARISONS AND MULTIPLICITY

The study requires both the primary safety and primary efficacy endpoints be met to declare study success, and therefore no multiplicity adjustment is required for declaring study success.

Also, given that the success standards are higher for both safety and efficacy for the supportive analyses than for the primary analyses, as long as statistical significance is achieved for the primary analyses, there is no statistical penalty required to make conclusions based on the more restrictive supportive analyses which are nested within the alternative hypotheses being tested.

7 ENDPOINT ANALYSES

7.1 PRIMARY EFFICACY VARIABLE

The primary efficacy endpoint is the percent of subjects in the ITT population with complete occlusion (defined as Raymond class I) without clinically significant stenosis (defined as $\geq 50\%$ stenosis) of the parent artery at the target IA based on core lab evaluations at the 12-month follow-up angiography and in whom an alternative treatment of the target IA had not been performed post-FRED placement. An alternative treatment is defined as re-treatment of the target aneurysm with an alternative treatment modality including open repair, endovascular

placement of an additional stent or treatment of In-stent Stenosis observed at the 180-day or 12 month follow-up time-points or at an unscheduled study follow up visit.

The primary efficacy hypotheses are:

$$H_{E0}: \pi_E \leq 0.45$$

$$H_{E1}: \pi_E > 0.45$$

The null hypothesis (H_{E0}) for this endpoint states that the true proportion of subjects treated with the FRED Device who achieve complete occlusion (Raymond class I) without clinically significant ($\geq 50\%$) stenosis of the parent artery 12 months post-treatment and without any subsequent alternative treatment is no higher than 45%. The alternative hypothesis the FRED trial aims to demonstrate is that the true proportion of subjects who achieve effectiveness success at 12 months is greater than 45%.

Using the prior

$$\pi_E \sim Beta(1,1)$$

the posterior distribution for the primary efficacy endpoint rate will be

$$\pi_E | E, n \sim Beta(1 + E, 1 + n - E)$$

where n is the number of evaluable subjects and E is the number of subjects who meet the efficacy endpoint. The point estimate of the posterior distribution of the primary efficacy endpoint will be presented with its lower 95% credible bound, as well as the posterior probability of the alternative hypothesis H_{E1} . If the posterior probability exceeds 0.95, the primary efficacy endpoint will have been met.

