Study Hypothesis	The safety and effectiveness of the FRED meets similar performance goal as that which was identified from a comprehensive analysis of the peer-reviewed published literature reporting the safety and efficacy of endovascular treatment of intracranial aneurysms with flow-diverter devices.
Primary Endpoint	
Primary Safety Endpoint: The primary safety endpoint is the proportion of subjects who experience one or more of the following:
 
 • death or major stroke within 30 days post procedure • neurological death or major ipsilateral stroke within 12 months post procedure 
 ➤ A major stroke is defined as a new neurological event that persists for > 24 hours and results in a \geq 4 point increase in the NIHSS score compared to baseline or compared to any subsequent lower score. ➤ A major ipsilateral stroke is defined as that occurring within the vascular distribution of the stented artery ➤ Neurologic death is defined as a death which has been adjudicated by the independent clinical events committee to have directly resulted from a neurologic cause 
Primary Effectiveness:
 
 • Proportion of subjects with complete occlusion (100%) of the target aneurysm and \leq 50% stenosis of the parent artery at the target IA at 12 months as assessed by angiography and in whom an alternative treatment of the target IA had not been performed within 12 months. 
 ➤ An alternative treatment is defined as re-treatment of the target aneurysm with an alternative treatment modality including open repair, endovascular placement of an additional stent or treatment of In-stent Stenosis observed at the 180 day or 12 month follow-up time-points or at an unscheduled study follow up visit.

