5.5 Study Endpoints and Success Criteria

Primary Endpoint(s):

1. The primary safety endpoint will consist of a composite of any/all of the events list below:

- death or major stroke within 30 days post procedure
- neurological death or major ipsilateral stroke within 12 months post procedure, measured by mRS and NIHSS.

NOTE: A major stroke is defined as a new neurological event that persists for > 24 hours and results in a ≥ 4 point increase in the NIHSS score compared to baseline or compared to any subsequent lower score. A minor stroke is defined as a new neurological event that persists for > 24 hours and results in an increase of < 4 points in the NIHSS score compared to baseline or compared to any subsequent lower score.

- A major ipsilateral stroke is defined as that occurring within the vascular distribution of the stented artery
- Neurologic death is defined as a death which has been adjudicated by an independent clinical events committee to have directly resulted from a neurologic cause

Neurological and functional assessments will be measured by comparing baseline scores at 30 days, 180 days and 12 months post procedure.

2. The primary effectiveness endpoint is:

Proportion of subjects with complete occlusion (100% occlusion) of the target aneurysm and $\leq 50\%$ stenosis of the parent artery at the target IA at 12 months as assessed by angiography and in whom an alternative treatment of the target IA had not been performed. An alternative treatment is defined as re-treatment of the target aneurysm with an alternative treatment modality including open repair, endovascular placement of an additional stent or treatment of In-stent Stenosis observed at the 180 day or 12 month follow-up time-points or at an unscheduled study follow up visit.

Secondary Endpoint(s):

1. Proportion of subjects with clinically acceptable (90-100%) occlusion of the target aneurysm, $\leq 50\%$ stenosis of the parent artery at the target IA at 12 months (+ 60 days, - 30 days) as assessed by angiography, and in whom an unplanned alternative treatment of the target IA had not been performed within 12 months. An alternative treatment is defined as re-treatment of the target aneurysm with an alternative treatment modality including open repair, endovascular placement of an additional stent or treatment of In-stent Stenosis observed at the 180 day or 12 month follow-up time-points or at an unscheduled study follow up visit.

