2. Proportion of subjects in whom an alternative treatment of the target IA had not been performed within 12 months
3. Proportions of subjects with clinically acceptable aneurysm occlusion (90 %-100 %) of the target aneurysm at 12 months (+ 60 days, -30 days)
4. Incidence of $\geq 50\%$ In-Stent Stenosis(ISS)at the target IA at 12 months as assessed by angiography at an independent corelab

5. Proportion of subjects with complete occlusion of the target aneurysm on 12-month angiography(+ 60 days, -30 days)
6. Incidence of FRED System procedure related Serious Adverse Events
7. Incidence of FRED System device related Serious Adverse Events;
8. Incidence of unsuccessful delivery of the FRED device
9. Incidence of unsuccessful deployment of the FRED device
10. Incidence of migration of the FRED device at 12 months
11. Unplanned alternative treatment on the target IA within 12 months defined as re-treatment of the target aneurysm with an alternative treatment modality including open repair, endovascular placement of an additional stent or treatment of In-stent Stenosis observed at the 180 day or 12 month follow-up time-points or at an unscheduled study follow up visit.
12. Incidence of change in clinical and functional outcomes at 180 days and 1 year follow up, as measured by an ≥ 3 point increase in the modified Rankin Scale due to neurologic disability as compared to baseline
13. Incidence of major stroke, as measured by NIHSS at 12-months (and ophthalmic examination related to the target aneurysm if determined appropriate)
14. Incidence of minor stroke, as measured by NIHSS at 12-months (and ophthalmic examination related to the target aneurysm if determined appropriate)

The statistical analyses of the primary and secondary endpoints of the study will be based on imaging data that has been reviewed and assessed by an independent core lab and on trial clinical data that has been reviewed and adjudicated by the independent Clinical Events Committee (CEC).

Study Success Criteria:

The criterion for success is based on the posterior probability of the alternative hypotheses for both efficacy and safety (i.e. both efficacy and safety being met).

Efficacy Criterion

The FRED System will be declared efficacious if the posterior probability of the alternative hypothesis H_A based on the primary efficacy endpoint for is large, that is

$$P(H_A|Data) = P(\pi_e > 45\%|Data) > \pi^*$$

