For efficacy, if the one-sided 95% lower credible interval is at least 45%, then efficacy is established. For safety, if the one-sided 95% upper credible interval is no more than 25%, then safety is established. Bayes logistic models will be used to compute the credible intervals controlling for age (<55, 55-64, ≥65) gender (male, female), zone (1, 2, 3), and region (Japan vs others). If both the safety and effectiveness null hypotheses are rejected, then the study goal will be considered to be met.

The primary effectiveness endpoint is defined, such that a subject will be considered a failure if the following occurs:

- A retreatment of the target aneurysm is required at any time prior to the 12-month follow-up evaluation, failure is considered to have occurred at the time of retreatment;
- The study device is deployed and properly positioned at the target site but fails to fully occlude the aneurysm by 12 months post-procedure;

Or if

- Presence of >50% stenosis of the parent artery at the target aneurysm at 12 months.

If a subject is a failure of this endpoint for multiple elements of the composite endpoint, then the subject is treated as a failure at the time of the earliest failure for the purposes of the statistical analysis.

Statistical Methods for Secondary Endpoints

The timing of the primary efficacy component failures (incomplete occlusion of the target aneurysm, >50% stenosis of the parent artery at the target IA at 12 months as assessed by angiography, an alternative treatment of the target IA was performed), primary safety components (death or major stroke within 30 days of the implant, death due to a neurological cause, major ipsilateral stroke through 12 months post implant) as well as the secondary endpoint proportions and incidences will be presented using standard summary statistics including the incidence and 95% credible intervals. No hypothesis tests will be performed for the primary or secondary endpoint components or secondary endpoints.

Adverse Events

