12.1.2 Parent Artery Patency

Stenosis shall be assessed using the WASID criterion which is defined as greater than 50% luminal loss at angiographic follow up using the WASID method:

$$[1(D_{\text{stenosis}}/D_{\text{normal}})] \times 100$$

Where D_{stenosis} is the diameter of the artery at the site of the most severe stenosis and D_{normal} is the diameter of the proximal normal artery.

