3.2 PRIMARY ENDPOINTS

Primary Safety Endpoint:

The primary safety endpoint is the proportion of subjects who experience one or more of the following:

- a. death or major stroke within 30 days post procedure
 - b. neurological death or major ipsilateral stroke within 12 months post procedure
- ✦ *A major stroke is defined as a new neurological event that persists for > 24 hours and results in a ≥ 4 -point increase in the NIHSS score compared to baseline or compared to any subsequent lower score.*
 - ✦ *A major ipsilateral stroke is defined as that occurring within the vascular distribution of the stented artery*
 - ✦ *Neurologic death is defined as a death which has been adjudicated by the independent clinical events committee to have directly resulted from a neurologic cause*

Primary Effectiveness Endpoint:

Proportion of subjects with complete occlusion of the target aneurysm utilizing the Raymond Scale and $\leq 50\%$ stenosis of the parent artery at the target IA at 12 months as assessed by angiography and in whom an alternative treatment of the target IA had not been performed within 12 months post-FRED placement; where an alternative treatment is defined as re-treatment of the target aneurysm with an alternative treatment modality including open repair, endovascular placement of an additional stent or treatment of In-stent Stenosis observed at the 180 day or 12 month follow-up time-points or at an unscheduled study follow up visit.

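### SAP 7.1 counts exactly 50% parent-artery stenosis as a primary-efficacy failure, while the protocol endpoint, the SAP's own definitions and the core-lab criterion do not

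*SAP*

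**What the plan says.** **Exactly 50% is acceptable, or not a failure:**
- Protocol Study Overview, primary effectiveness: "\leq 50% stenosis of the parent artery at the target IA at 12 months as assessed by angiography". Protocol 5.5 and the endpoint text in 6.2 use the same limit.
- Protocol 6.2, failure list: "Presence of >50% stenosis of the parent artery at the target aneurysm at 12 months". The list of component failures under the secondary-endpoint methods also uses above 50%.
- Protocol 12.1.2, core-lab stenosis criterion: "defined as greater than 50% luminal loss at angiographic follow up".
- Protocol 5.1 describes major stenosis as above 50%, both for this trial and for the comparator device's trial.
- SAP Summary and SAP 3.2: the definition in 3.2 begins "Proportion of subjects with complete occlusion of the target aneurysm utilizing the Raymond Scale and" and continues with stenosis of at most 50%.

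**Exactly 50% is a failure:**
- SAP 7.1, variable definition: success is complete occlusion "without clinically significant stenosis (defined as", and the limit that follows is 50% or more.
- SAP 7.1, wording of the null hypothesis: 50% or more again.

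**Secondary endpoint 4.** The Protocol Study Overview counts subjects with in-stent stenosis of at most 50%. Protocol 5.5 counts the incidence of 50% or more ("In-Stent Stenosis(ISS)at the target IA at 12 months as assessed by angiography at an independent corelab"), as do both SAP lists (Summary and 3.4).

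**The concern.** SAP 7.1 is where the count E in the Beta posterior is defined. A programmer working from it would apply a different endpoint from the one in the protocol and in SAP 3.2. Because 7.1 states its limit twice, a reader cannot safely dismiss it as one mistyped sign. No sentence announces a deliberate change or gives one section precedence.

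SAP 7.1 also rests on core-lab evaluations, and the stated core-lab criterion is above 50%. If the core lab returned only above or not above 50%, the rule in 7.1 could not be applied. The documents do not say how readings are recorded.

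At stake is the integrity of the pre-specification. In a single-arm trial judged against a fixed goal, two written rules for one endpoint allow the choice between them to be made after outcomes are known. The supportive analysis against 46% uses the same variable and inherits the ambiguity.

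**Working it through.** **1. One subject under each rule.** Take complete occlusion, no alternative treatment and stenosis of exactly 50%.

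| Source | Rule | Result |
|---|---|---|
| Protocol Study Overview, 5.5, 6.2 endpoint text | at most 50% | success |
| SAP Summary, SAP 3.2 | at most 50% | success |
| Protocol 6.2 failure list | fails if above 50% | not a failure |
| Protocol 12.1.2 core-lab criterion | stenosis if above 50% | not stenotic |
| SAP 7.1 definition and null hypothesis | fails if 50% or more | failure |

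Readings above 50% fail, and readings below 50% pass the stenosis component, under every rule. Only exact equality is in dispute. Because the endpoint is composite, equality matters only in subjects who meet the other two components.

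**2. The plan's own power figure.** The table in SAP 7.2 gives 90% for N = 140, null 0.45, alternative 0.58, one-sided alpha 0.05. The exact binomial test needs at least 74 of 140; P(X ≥ 74 | 0.45) = 0.0375 and P(X ≥ 74 | 0.58) = 90.6%. The stated figure is reproduced. The Beta(1,1) posterior rule in SAP 7.1 needs at least 73 of 140 and gives 93.1%. None of these figures depends on the stenosis limit.

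**3. Effect of one reclassified subject.** SAP 7.1 gives the posterior Beta(1 + E, 1 + n − E), with success if P(π > 0.45) exceeds 0.95. The SAP states n as 145 (Summary, Study Design) and as 140 (7.2), so both are shown.

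| n | One subject | E that fails (posterior) | E that passes (posterior) |
|---|---|---|---|
| 145 | 1/145 = 0.69 points | 75 (0.948) | 76 (0.963) |
| 140 | 1/140 = 0.71 points | 72 (0.937) | 73 (0.955) |

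**4. How likely it is that one subject decides.** At the SAP's alternative, 145 × 0.58 = 84.1 successes are expected, about eight above the cut-off of 76. The chance of landing on exactly 76, where losing one subject reverses the result, is P(X = 76 | 145, 0.58) = 2.6%. At the protocol's planning rate of 56.5% it is 4.1%. Reversal also needs an exact-50% reading in an otherwise successful subject.

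**5. Range under an assumption.** The documents give no frequency for readings of exactly 50%. Suppose a share f of all subjects are otherwise successful and read at exactly 50%. Power at N = 140 under the posterior rule, with the true rate falling from 0.58 to 0.58 − f, is:

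| f (assumed) | Expected subjects (140 × f) | Power |
|---|---|---|
| 0 | 0 | 93.1% |
| 0.5% | 0.7 | 91.4% |
| 1% | 1.4 | 89.3% |
| 2% | 2.8 | 84.2% |
| 3% | 4.2 | 77.8% |

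**The case against.** The strongest reply is that this is a difference of one sign that may touch no subject at all. Stenosis in Protocol 12.1.2 is computed from two measured diameters, so exact equality could be rare. That a single subject can decide near a threshold is true of any binary rule, and at the planned rate the trial expects to clear the cut-off comfortably. This stands as to size.

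Three stronger readings are tempting, and the documents do not support them:
- *The 3.8% literature in-stent stenosis rate in Protocol 5.1 implies about five affected subjects.* That rate is given without a threshold or a distribution of readings. Subjects above 50% fail under both rules, so it says nothing about exact equality.
- *Readings cluster at 50% because they are rounded.* Protocol 12.0 calls the image analysis qualitative, but no document describes rounding or categorical reporting. Rounding would be an assumption.
- *The clash inflates false success.* SAP 7.1 is the stricter rule. Following it can cost a success but cannot create one.

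On secondary endpoint 4, the reply is that 50% or more appears consistently in Protocol 5.5 and both SAP lists, that only the Study Overview differs, and that no hypothesis test is attached. This also stands: there is more than one way to reconcile that endpoint.

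None of this removes the contradiction in the primary endpoint.

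**Conclusion.** The plan is wrong as written. Current text gives two opposite rules for the primary efficacy outcome at exactly 50% stenosis, and SAP 7.1, the section that defines the analysed count, is the one that departs from the rest.

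The size is about 0.7 percentage points per affected subject, counting only subjects with complete occlusion and no alternative treatment. The number affected is unknown and probably small, so the conclusion would be unlikely to change if the true rate is near the planned 56.5% to 58%. The illustrated power loss rests wholly on assumed shares.

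The case for acting does not rest on size or on bias toward success. It rests on closing a choice that could otherwise be made with the data in view. Secondary endpoint 4 is a separate, descriptive matter: its two versions are not complements, because exactly 50% is counted in both.

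**What to change.** Before analysis, change both statements in SAP 7.1 (the variable definition and the null-hypothesis wording) so that stenosis above 50% is the failure. This matches SAP 3.2, Protocol 5.5 and 6.2, and the core-lab criterion in Protocol 12.1.2. It is a wording change to the SAP and alters no sample size, alpha or stated power.

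Separately, give secondary endpoint 4 one cut-off. Using above 50% makes it the exact complement of the Study Overview version and agrees with the primary endpoint, but it needs edits to Protocol 5.5 as well as to the SAP Summary and SAP 3.4. Keeping 50% or more and changing the Study Overview to below 50% would also reconcile the text, at the price of a cut-off different from the primary endpoint's.

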6.2 Proposed Sample Size and Data Analysis

Upon FDA approval of CL12001 Rev 3.0, enrollment will be increased from 127 to 195 to allow for enrollment of subjects using FRED line extension. Sample size was determined through simulations. The sample size was chosen so that the Type I and the Type II error rates are bounded. With 155 subjects, there will be 80% posterior probability to reject the 45% OPC null hypothesis for efficacy and the 25% OPC null hypothesis for safety using one-sided tests with 5% Type I error.

Simulations were run in R statistical package (R citation) and OpenBUGS software, version 3.2.2. For each scenario, 10,000 datasets were generated in R. OpenBUGS was then used to obtain samples from the posterior distribution of each parameter and to calculate the probability of success. For each analysis, 50,000 samples were obtained from the posterior distributions after 1,000 samples were discarded.

Primary Efficacy

The primary efficacy endpoint in this study is complete occlusion of the target aneurysm and $\leq 50\%$ stenosis of the parent artery at the target IA at 12 months as assessed by angiography and in whom an alternative treatment of the target IA had not been performed. An alternative treatment is defined as re-treatment of the target aneurysm with an alternative treatment modality including open repair, endovascular placement of an additional stent or treatment of In-stent Stenosis observed at the 180 day or 12 month follow-up time-points or at an unscheduled study follow up visit.

The study is designed to compare the primary efficacy success percent to an independently derived performance goal, which is 45% for efficacy. The performance goal was obtained from a formal meta-analysis of results from studies of flow diverters during the first year after treatment. The methods and results of this meta-analysis are described in detail in the appendix. The null and alternative hypotheses are:

Null hypothesis: $P_e \leq 45\%$

Alternative hypothesis: $P_e > 45\%$,

where P_e is the proportion of subjects that are successes for the primary efficacy endpoint.

Allowing for up to 20% attrition through 12 months, a sample size of at least $N=155$ is expected at 12 months. Should the FRED percent equal 56.5%, then the sample size of 155 subjects would reject the null hypothesis with 80% power and one-sided 5% alpha level.

Primary Safety

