The primary safety outcome is the percent of subjects who experience death or major stroke within 30 days of the implant or death due to a neurological cause or major ipsilateral stroke through 12 months post implant. The study is designed to compare the primary safety percent to an independently derived performance goal, which is 25% for safety. The null and alternative hypotheses are:

Null hypothesis: $P_s \geq 25\%$

Alternative hypothesis: $P_s < 25\%$,

where P_s is the proportion of subjects with primary safety endpoint events.

The performance goal used in the P100018 SSED of the Pipeline PUFs study was 20%. However, the definition used in the PUFs study did not include all death and major stroke within 30 days, only death of neurologic cause and major ipsilateral strokes, and it was only evaluated through 180 days, not 12 months. For this reason, the performance goal utilized here is slightly higher. The primary safety endpoint in this study has not been used or reported as such previously, so the magnitude of the effect of this change is unknown. For the purposes of the current study a conservative 5% adjustment is used, resulting in a 25% performance goal (20% from above + 5% conservative adjustment). Should the FRED primary safety endpoint percent equal 15%, then the sample size of $N=155$ subjects would reject the null hypothesis with >80% power and one-sided 5% alpha level.

Statistical Methods for Primary Endpoints

The primary safety and effectiveness endpoints will be analyzed using Bayes models (OpenBUGS). The proposed model is a beta-binomial model that assumes that the outcome is a Binomial variable and a uniform prior on the probability of event.

Likelihood:

The likelihood is constructed based on distributional assumptions on the safety and efficacy results of the FRED system.

With N_e and N_s being the number of evaluable subjects for the Efficacy and Safety endpoints, respectively, the number of subjects that are successes for the primary efficacy endpoint, y_e , and the number of subjects with primary safety endpoint events are assumed to follow Binomial distribution with respective rates π_e and π_s . Thus,

$$y_e \sim \text{Binomial}(\pi_e, N_e) \text{ and } y_s \sim \text{Binomial}(\pi_s, N_s).$$

Prior Distributions:

Uninformative prior distributions are assumed for the efficacy and safety rates. More precisely,

$$\pi_e \sim \text{Beta}(1,1) \text{ and } \pi_s \sim \text{Beta}(1,1).$$

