Study Design	
A multi-center, prospective, single-arm study with follow-up at discharge, 30 days (± 7 days), 180 days (± 30 days) and 12 months (+ 60 days, -30 days). Data will be analyzed according to nominal visit, e.g. 30 days, 180 days, 12 months as opposed to actual date.
 
The intent-to-treat (ITT) population as defined below will be the primary population for all efficacy analyses and the safety population for all safety analyses. One hundred forty-five (145) subjects will constitute the ITT cohort, which is identical to the Safety cohort. These subjects were enrolled and treated at 23 sites located in United States and Japan.
 
Subjects are included in study analyses consistent with the prospective literature control, with efficacy and safety objective performance criteria (OPCs) used to determine sample size.
 
Two OPC sets will be considered in support of efficacy and safety as per the original protocol (primary) as well as more strict (supportive) OPCs as follows:
 
 • Primary: Original PG specified in the protocol (45% for efficacy and 25% for safety) • Supportive: Updated PG presented to FDA at the Feb 2017 meeting (46% for efficacy and 15% for Safety). 
Study success is defined as achieving statistical significance for the primary OPCs.
 
Primary Analyses: The powers will be 80% to rule out a 45% OPC (efficacy) margin (lower bound) and 80% to rule out a 25% OPC (safety) margin (upper bound) using one-sided tests. The trial will be considered successful if the one-sided 95% credible lower bound of the efficacy rate exceeds the 45% OPC and the one-sided 95% credible upper bound of the safety rate is below the 25% OPC. The use of one-sided testing is consistent with the protocol.
 
Supportive Analyses: The powers will be 90% to rule out a 46% OPC (efficacy) margin (lower bound) and 90% to rule out a 15% OPC (safety) margin (upper bound) using two-sided tests. The trial will be considered successful if the two-sided 95% credible lower bound of the efficacy rate exceeds the 46% OPC and the two-sided 95% credible upper bound of the safety rate is below the 15% OPC. The use of two-sided testing is consistent with the PIPELINE PMA and FDA guidance.

Follow-Up Schedule	All enrolled and treated subjects had follow up scheduled at 30 day (± 7 days), 180 days (± 30 days), and 12 months (+ 60 days, -30 days).
Interim Analyses	No interim analysis are planned.

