7.2 PRIMARY SAFETY ENDPOINT

The study's primary safety endpoint is the proportion of subjects in the Safety Population who experience either major stroke or death within 30 days, or major ipsilateral stroke or neurological death 31 days through 12 months post procedure. CEC-adjudicated data will be used for this analysis.

The primary safety hypotheses are:

$$H_{S0}: \pi_S \geq 0.25$$

$$H_{S1}: \pi_S < 0.25$$

The null hypothesis (H_{S0}) for this endpoint states that the true proportion of subjects treated with the FRED Device who experience neurologic death or major ipsilateral stroke one-year post-treatment is equal to or higher than 25%. The alternative hypothesis the FRED trial aims to demonstrate is that the true proportion of subjects treated with the FRED Device who experience neurologic death or major ipsilateral stroke one-year post-treatment is actually lower than 25%.

Using the noninformative prior

$$\pi_S \sim \text{Beta}(1,1)$$

the posterior distribution for the primary safety endpoint event rate will be

$$\pi_S | S, n \sim \text{Beta}(1 + S, 1 + n - S)$$

where n is the number of evaluable subjects and S is the number of subjects who meet the safety endpoint. The point estimate of the posterior distribution of the primary safety endpoint will be presented with its lower 95% credible bound, as well as the posterior probability of the alternative hypothesis H_{S1} . If the posterior probability exceeds 0.95, the primary safety endpoint will have been met

The supportive analysis (second OPC set) will be conducted for both primary efficacy and primary safety using more restrictive performance goals identified from a revised set of literature analysis and presented to FDA on 16 February 2017. The format of this analysis will be a Bayesian design identical in form to the above except that the performance goals will be 0.46 for efficacy and 0.15 for safety. Details of the resulting analyses and associated power are as below, from which it can be seen that the study is sufficiently powered at the final enrolled and treated count of 140.

	Efficacy		Safety	
	Original	Revised	Original	Revised
Significance level, alpha	0.05	0.025	0.05	0.025
1 or 2-sided test	1	1	1	1
Null: OPC, p_0	0.45	0.46	0.25	0.15
Alternative: FRED, p_A	0.58	0.60	0.15	0.06
Power (%)	90	90	90	92
N	140	140	140	140

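### The efficacy columns of the SAP 7.2 table do not describe the planned Beta(1,1) rule: at N=140 its Type I error is 5.36% and 3.01%, and its power 93.1% and 92.8%

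*SAP*

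**What the plan says.** **The rule.** Protocol 6.2: "The proposed model is a beta-binomial model that assumes that the outcome is a Binomial variable and a uniform prior". Protocol 5.5 sets the posterior bound at 0.95 for efficacy and safety, and requires both. SAP 7.1 gives the posterior as Beta(1+E, 1+n−E), where n is the evaluable count and E the successes, and adds: "If the posterior probability exceeds 0.95, the primary efficacy endpoint will have been met". SAP 7.2 gives the supportive analysis the same form, with goals of 46% and 15%. SAP 4.3 judges it on a two-sided 95% credible bound, which is a posterior cut-off of 0.975.

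**The stated error rates and power.** Protocol 6.2 says that both error rates are bounded. It gives 80% for rejecting the efficacy and safety nulls with 155 subjects, "using one-sided tests with 5% Type I error". For efficacy alone, at a true rate of 56.5%, it says: "then the sample size of 155 subjects would reject the null hypothesis with 80% power and one-sided 5% alpha level". The basis is simulation: "For each scenario, 10,000 datasets were generated in R". SAP 7.2 tabulates efficacy alpha 0.05 and 0.025 with power 90 and 90, and concludes that "the study is sufficiently powered at the final enrolled and treated count of 140". SAP 1 and SAP 4.3 give 80% for the primary analyses, with no N or alternative rate.

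**What is left open.** Protocol 6.2 also says: "Bayes logistic models will be used to compute the credible intervals controlling for age", together with gender, zone and region. SAP 7.1 contains no such model. SAP 6.6 and 7.3 allow missing 12-month efficacy outcomes to be filled from 6-month results, including by conditional probabilities. SAP 1 says: "One hundred forty-five (145) subjects will constitute the ITT cohort, which is identical to the Safety cohort", whereas SAP 7.2 uses 140.

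**The concern.** Once the prior, the cut-off and n are fixed, the rule has one critical count, and hence an exact Type I error and an exact power at any true rate. The figures that the documents attach to it can therefore be checked without outside information. For efficacy they appear to belong to a different test.

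The primary rule decides the efficacy half of study success, and the supportive rule backs the labelling claims that SAP 4.3 intends to seek. A result of exactly 73/140 would meet the criterion while its exact one-sided binomial p-value is 0.0536. That invites a dispute after the fact, which stating the critical count beforehand would avoid.

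**Working it through.** **Inputs.** Null rates 0.45 and 0.46 (efficacy), 0.25 and 0.15 (safety); alternatives 0.58 and 0.60, 0.15 and 0.06; N=140 (all from the SAP 7.2 table). N=155 and 56.5% come from protocol 6.2. Prior and cut-offs are as above.

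**Step 1: reproduce the table.** The smallest r with P(Bin(140, p0) ≥ r) ≤ alpha is 74 for 0.45 and 77 for 0.46, giving power 90.6% and 90.2%. The same exact test for safety allows at most 26 and 12 events, giving 90.1% and 92.1%. All four are within 0.6 points of the tabulated 90, 90, 90, 92. A continuity-corrected normal formula also comes near for efficacy (91.5%, 90.3%) but less so for safety (88.5%, 91.3%). The SAP names no method, so the exact binomial origin is an inference.

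**Step 2: apply the planned rule.** For efficacy, c = min{E : P(Beta(1+E, 1+n−E) > p0) > cut-off}; Type I error = P(Bin(n, p0) ≥ c); power = P(Bin(n, pA) ≥ c).

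| Rule | n | c | Posterior at c | Type I error (stated) | Power (stated) |
|---|---|---|---|---|---|
| Primary, 45%, 0.95 | 140 | 73 | 0.9552 | 5.36% (5%) | 93.1% at 58% (90%) |
| Supportive, 46%, 0.975 | 140 | 76 | 0.9752 | 3.01% (2.5%) | 92.8% at 60% (90%) |
| Primary, 45%, 0.95 | 155 | 80 | 0.9510 | 5.80% (5%) | 90.4% at 56.5% (80%) |

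At 140 the posterior rule asks for one success fewer than the exact test (73 against 74; 76 against 77). That single success accounts for both the higher power and the Type I error above nominal.

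**Step 3: safety.** The posterior rule at N=140 allows 26 and 12 events, the same as the exact test: Type I error 4.53% and 1.70%, power 90.1% and 92.1%. These columns match the planned rule.

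**Step 4: dependence on n.**

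| n | Primary c | Type I error | Supportive c | Type I error |
|---|---|---|---|---|
| 140 | 73 | 5.36% | 76 | 3.01% |
| 141 | 74 | 4.48% | 77 | 2.48% |
| 142 | 74 | 5.30% | 77 | 3.01% |
| 143 | 75 | 4.43% | 78 | 2.48% |
| 144 | 75 | 5.24% | 78 | 3.01% |
| 145 | 76 | 4.39% | 79 | 2.48% |

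Over n=112 to 155 the primary efficacy error runs from 4.16% to 6.04%, with mean 5.05%. Safety oscillates too: it is 5.24% and 2.58% at n=143.

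**Step 5: joint rates, assuming that efficacy and safety are independent.** At N=155, with true rates of 56.5% and 15%, joint power is 0.9043 × 0.9169 = 82.9%. With efficacy at its null and true safety at 15%, the chance of declaring study success is 5.36% × 90.1% = 4.8% at N=140, and 5.80% × 91.7% = 5.3% at N=155.

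**The case against.** The strongest reply is that a posterior cut-off of 0.95 does not promise a frequentist size of 5% at every n, that alpha in the table can be read as nominal, and that the rule averages 5.05%. Study success also needs safety, which brings the N=140 rate to about 4.8% under the assumptions of step 5. If all 145 ITT subjects are evaluable, both efficacy rules meet their nominal levels. All of that stands, and it limits the point to a correction. It does not remove it. Protocol 6.2 claims bounded errors and a 5% Type I error, SAP 7.2 presents its table as details of the Bayesian analyses, and n is the evaluable count, so a single subject lost from 145 returns the rates to 5.24% and 3.01%.

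Protocol 6.2's first 80% statement may mean joint power, which fits (82.9%). Its later efficacy-only statement does not fit (90.4%).

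A reader might infer more: that the trial fails to control its false-positive rate, that the cut-offs must be raised, or that the protocol's simulation was done wrongly. The documents support none of these. The excess is one success at some n and none at others. The simulation output is not given, nor is it said which rule was simulated. The boundary posterior at 80/155 is 0.9510, while 50,000 draws carry a standard error of about 0.001 if independent, so a simulated error nearer 5.5% would be expected even from a correct run.

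**Conclusion.** The point holds as a minor error in stated operating characteristics. At N=140 the Type I error exceeds the stated level by 0.36 points (primary) and 0.51 points (supportive), and power is understated by 3.1 and 2.8 points. At N=155 the excess is 0.80 points, and efficacy-only power is understated by 10.4 points. The power error is conservative, and the SAP's conclusion that 140 is enough is not disturbed.

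These figures rest on the unadjusted beta-binomial rule with integer E. If the covariate-adjusted logistic model governs, or conditional probabilities enter E, the error rate cannot be derived from the documents. The difference between 140 and 145 subjects is a separate discrepancy.

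**What to change.** Keep the decision rule and revise the SAP before outcomes are analysed, in this order.

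1. State whether the unadjusted beta-binomial rule of SAP 7.1 or the covariate-adjusted logistic model of protocol 6.2 governs the success decision, and how imputed 12-month outcomes enter E and n.
2. If the beta-binomial rule governs, restate the SAP 7.2 efficacy cells at N=140: count 73, Type I error 5.36%, power 93.1%; supportive 76, 3.01%, 92.8%. Add N=145: 76, 4.39%, 92.55%; supportive 79, 2.48%, 92.45%. Name the method and label alpha as nominal.
3. Reconcile the 80% primary power in SAP 1 and SAP 4.3 with the table, giving the N and alternative rate to which each figure belongs.
4. Record in the SAP, as a correction to the planning statement of protocol 6.2, the N=155 figures: Type I error 5.80% and efficacy-only power 90.4% at 56.5%.
5. State the critical count for the final evaluable n: 73, 74, 74, 75, 75, 76 for n=140 to 145 (supportive 76, 77, 77, 78, 78, 79).

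If the beta-binomial rule governs, the cost is SAP text only; no success criterion or sample size changes. The downside is that the SAP will show a Type I error slightly above nominal at some n. If the logistic model is chosen, items 2, 4 and 5 need its own operating characteristics instead.
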